### All Adverse Events (AEs)

#### Treatment-emergent Adverse Event

A TEAE is defined as an AE that began after the start of trial medication treatment or if the event was continuous from baseline and was serious, trial medication-related, or resulted in death, discontinuation, or interruption or reduction of trial therapy, those TEAEs will be analysed for the purpose of safety analysis.

#### 4.12.2 Deaths, Serious Adverse Events, and Other Significant Adverse Events

The following summary tables will be provided.

- Summary of all-cause mortality - Number of subjects and occurrences by SOC & PT
- Summary of serious adverse events - Number of subjects and occurrences by SOC & PT

The following listings will be provided.

- A by participant listing of all deaths that occurred during the study
- A by participant listing of all SAEs
- A by participant listing of all TEAEs leading to discontinuation of study treatment

#### 4.12.3 Clinical Laboratory Evaluation

Clinical laboratory test results of haematology, clinical chemistry, coagulation, pregnancy testing and other screening tests (FSH and oestradiol as needed in WONCBP only, urine alcohol and drug screen, serology) will be provided by subject. A list of current reference ranges of laboratory assessments is included in Section 6.3. Since laboratory ranges can be subject to changes over time the reference ranges presented in Section 6.3 might differ from the ones used and presented on SDTM. For analysis purposes only the ranges present on the SDTM will be used.

All TLFs will display only the standard international (SI) units after conversion by means of standard conversion factors.

Quantitative clinical laboratory variables, ie, haematology, clinical chemistry, and coagulation will be summarized using descriptive statistics (n, mean, SD, minimum, maximum and median) by on/off treatment. Additionally, a within-participant change will be calculated as the post-baseline measurement minus the baseline measurement and summarized in the same way.

Baseline definition will be defined in section [4.2.4](#).

Each laboratory result will be classified as low (L), normal (N), or high (H) at each time point according to the laboratory supplied reference ranges. Tabulations will be presented by treatment (on/off treatment).

Measurements obtained at Screening and EOS will not be included in the shift tables.

Frequency tabulations of qualitative clinical laboratory variables will be presented by treatment (on/off treatment).

All laboratory data will be displayed in listings.

Laboratory abnormalities that are considered clinically significant (CS) are recorded in the database as AEs. Therefore, no tabulation of laboratory values meeting any CS criteria will be presented as all relevant information will be presented in the AE summaries.

Results of pregnancy tests (females only), serology, alcohol and drug of abuse tests will be listed only.

#### 4.12.4 Vital Signs

A by-participant listing of all vital sign measurements (including weight) and change from baseline will be presented.

Baseline will be defined in section [4.2.4](#).

Measured (observed) values including changes from baseline will be summarized by on/off treatment and by vital sign parameter (pulse rate, systolic and diastolic blood pressure, and oral body temperature).

Individual clinically significant vital sign values that were considered AEs by the PI will be presented in the AE listings.

#### 4.12.5 12-lead ECG

Standard 12-lead ECG will be obtained as outlined in the SoA (Table 6-1) using an ECG machine that automatically calculates the heart rate. All ECGs in this study should all be recorded using the same make of ECG device (Mortara Surveyor Telemetry Central and Mortara telemetry transmitters Model: Surveyor S4), with the exception of Screening visit, where CardioSoft® will be used. The Mortara system is validated every 12 months. Monitors will also be available to spot check the calibration when on-site. The readings generated by Mortara surveyor S4 machine will be validated by the cardiologist with their interpretation on whether the findings are significant and related to paroxetine. ECGs must be recorded after 10 minutes rest in the supine position to ensure a stable Baseline. ECGs will be performed and recorded in the eCRF at the times shown in SoA (Table 6-1). The preferred sequence of cardiovascular data collection during study visits is ECG collection first, followed by vital signs, blood sampling, and any remaining assessments for that visit.

At Screening, participants will be excluded based on ECG measurements if the resting QTc is  $>450$ msec (mean of three twelve-lead ECG measurements and using Fridericia's correction). The Fridericia QT correction formula (QTcF) must be used for clinical decisions, e.g., at Screening to assess eligibility. Further, all ECGs will be performed in triplicate collected within 5 min, at least 1 minute in between, at each timepoint.

- Triplicate ECGs will be performed at each timepoint as detailed in SOA (Table 6-1). The mean QTc value will be calculated from the triplicate ECGs for each participant.
- The ECG extractions will be paired with paroxetine concentration samples but will be obtained before the actual paroxetine concentration sampling time to avoid changes in autonomic tone associated with the psychological aspects of blood collection as well as the reduction in blood volume subsequent to blood collection.
- At visits where an ECG is not scheduled, an ECG can be performed if medically indicated.

- All ECG traces will be measured by a third-party vendor, which includes review by a licensed cardiologist. The cardiologist will review the ECGs and provide interpretation on whether the findings are normal, abnormal but non-clinically significant, or abnormal but clinically significant.
- A qualitative interpretation of the ECG will be performed by the cardiologist (according to the charter referenced as "Charte\_Cardiabase\_v5.7\_2019-02-12\_AtriumV7"). This morphological interpretation will provide a codification of the abnormalities detected on the recordings according to a code list grouping the abnormalities such as Q or Qs pattern, T/U wave abnormalities, Rhythm, etc.
- More than one cardiologist from the vendor may be reviewing the ECGs in the study. However, to remove bias all ECGs of a particular participant will be reviewed by the same cardiologist. The cardiologists will also be blinded to study visits/timestamps/paroxetine dose at which the ECGs were performed. A copy should be filed in the participant's medical records. Any clinically significant finding observed on the ECG should be recorded as an AE. A copy of ECG traces (with participant-identifying details redacted) may be collected by a Sponsor appointed representative for additional cardiology review if required. Clinically significant abnormalities must be recorded on the eCRF as either medical history/current medical conditions or adverse events as appropriate.

The ECG will be evaluated by the Investigator as 'Normal', 'Abnormal, NCS' or 'Abnormal, CS'. All ECG parameters will be listed by participant including changes from baseline.

Baseline is defined in section [4.2.4](#).

If ECGs measurements are performed in triplicate, then mean of the triplicates will be presented in the listing and used for deriving baseline and changes from baseline.

Descriptive statistics for absolute values and changes from baseline will be presented by visit/ dose level and time point. Two-sided 90% confidence interval of the mean will also be calculated on changes from baseline.

Time course of mean changes from baseline with 90% confidence interval of the mean will be presented by dose level.

A summary of the number and percentage of participants per visit/dose level with ECG intervals exceeding some predefined limits (eg, >450 msec, >480 msec, >500 msec for measured values as well as, >30 msec, >60 msec for changes from baseline for QTc intervals will be displayed in a frequency table. All thresholds for the categorical analysis are presented in Section 6.4. Values meeting the thresholds for abnormality will be flagged in the individual data listings.

A summary of the number and percentage of participants per visit/dose level with at least one treatment emergent morphological abnormality will be displayed in a frequency table. Treatment-emergent abnormality will be defined as any abnormality not already reported on any of the baseline ECGs.

The listing of ECG abnormalities will be presented separately.

The listing of morphological ECG abnormalities will be presented separately.

If ECGs measurement are performed in triplicate, only the mean of the triplicates will be presented in the listing and used for deriving baseline and change from baseline.

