### 8.3.3. Electrocardiograms

Standard 12-lead ECG will be obtained as outlined in the SoA (Table 2) using an ECG machine that automatically calculates the heart rate. All ECGs in this study should all be recorded using the same make of ECG device (Mortara Surveyor Telemetry Central and Mortara telemetry transmitters Model: Surveyor S4), with the exception of Screening visit, where CardioSoft® will be used. The Mortara system is validated every 12 months. Monitors will also be available to spot check the calibration when on-site. The readings generated by Mortara surveyor S4 machine will be validated by the cardiologist with their interpretation on whether the findings are significant and related to paroxetine. ECGs must be recorded after 10 minutes rest in the supine position to ensure a stable Baseline. ECGs will be performed and recorded in the eCRF at the times shown in Table 2. The preferred sequence of cardiovascular data collection during study visits is ECG collection first, followed by vital signs, blood sampling, and any remaining assessments for that visit.

At Screening, participants will be excluded based on ECG measurements if the resting QTc is >450msec (mean of three twelve-lead ECG measurements and using Fridericia's correction). The Fridericia QT correction formula (QTcF) must be used for clinical decisions, e.g., at Screening to assess eligibility. Further, all ECGs will be performed in triplicate collected within 5 min, at least 1 minute in between, at each timepoint.

- Triplicate ECGs will be performed at each timepoint as detailed in SOA (Table 2). The mean QTc value will be calculated from the triplicate ECGs for each participant.

- The ECG extractions will be paired with paroxetine concentration samples but will be obtained before the actual paroxetine concentration sampling time to avoid changes in autonomic tone associated with the psychological aspects of blood collection as well as the reduction in blood volume subsequent to blood collection.
- At visits where an ECG is not scheduled, an ECG can be performed if medically indicated.
- All ECG traces will be measured by a third-party vendor, which includes review by a licensed cardiologist. The cardiologist will review the ECGs and provide interpretation on whether the findings are normal, abnormal but non-clinically significant (unrelated to Paroxetine), or abnormal but clinically significant (related to paroxetine).

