**6.4 ECG Notable Criteria**

Parameter	Definition/threshold	Flag for listings
QTcF, QTcB (msec)	QTc Value >450 and $\leq$ 480 msec QTc value >480 and $\leq$ 500 msec QTc value >500 msec QTc increase > 30 and $\leq$ 60 msec QTc increase >60 msec	B H P I I+
HR (beats/min)	HR<40 beats/min HR>120 beats/min HR relative change >25%	L H I
PR (msec)	PR>220 msec PR relative change >25%	H I
QRS (msec)	QRS relative change >25% QRS>120 msec	I H

Flagging system will be used in listings to identify values meeting thresholds, also not necessarily related to clinically significant events, the flags can be interpreted as follows:

L: Low value - B: Borderline value - H: High value - P: Prolonged value

I: Noticeable increase from baseline - I+: marked increase from baseline.

QTc correspond to both QTcF and QTcB

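### The SAP's ECG outlier table counts participants above the trial's own entry limits without separating those already above the limit on drug-free Day -1 from new exceedances

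*SAP*

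**What the plan says.** **Entry.** Protocol 5.1, inclusion criterion 6, requires QTcF below 450 msec, PR of at most 220 msec and QRS below 120 msec, on the mean of one Screening triplicate. Protocol 8.3.3 repeats the QTc rule: "participants will be excluded based on ECG measurements if the resting QTc is >450msec", using Fridericia's correction. No entry limit is set for Bazett-corrected QTc.

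**Outlier table.** SAP 4.12.5 plans a frequency table of the "number and percentage of participants per visit/dose level with ECG intervals exceeding some predefined limits" and adds that "All thresholds for the categorical analysis are presented in Section 6.4". The lowest QTc band in SAP 6.4 starts at "QTc Value >450 and" up to 480 msec, with higher bands above 480 and above 500. The other interval limits are "PR>220 msec PR relative change >25"% and "QRS relative change >25% QRS>120 msec". A note says "QTc correspond to both QTcF and QTcB". The table also includes QTc increases of more than 30 and more than 60 msec.

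**Morphology.** The next paragraph of 4.12.5 tabulates treatment-emergent morphological abnormalities: "Treatment-emergent abnormality will be defined as any abnormality not already reported on any of the baseline ECGs". No such condition is attached to the absolute interval limits.

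**The concern.** Eligibility rests on one Screening triplicate, taken with a different ECG system (CardioSoft) from all later recordings (Mortara). Each serial visit then gives 12 triplicate means. The SAP names no single timepoint for the outlier count, so the natural reading is that one exceedance at any of the 12 is enough. A participant admitted just below a limit can cross it by ordinary variation, and may already have crossed it on Day -1.

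The study is single-arm, so Day -1 is the only drug-free reference. If the counts on Days 7, 14 and 21 mix pre-existing with new exceedances, a reader cannot tell from the table how many participants first exceeded the limit on paroxetine. With 36 participants, each one is 1/36 = 2.8 percentage points.

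**Working it through.** The plan states no expected outlier rate and no ECG standard deviation, so there is no planned figure to reproduce.

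**1. Limits side by side**

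| Interval | Entry (Protocol 5.1, 8.3.3) | Lowest absolute limit (SAP 6.4) | Day -1 condition |
|---|---|---|---|
| QTcF | <450 msec | >450 msec | none |
| QTcB | none | >450 msec | none |
| PR | ≤220 msec | >220 msec | none |
| QRS | <120 msec | >120 msec | none |
| Morphology | – | any coded abnormality | not on any baseline ECG |

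**2. Chance of crossing a limit with no drug effect**

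Let m be the distance from a participant's true mean to the limit, in within-participant SDs of a triplicate mean. With k independent readings, P(at least one above) = 1 − Φ(m)^k. The SoA gives k = 12 per visit and 36 over Days 7, 14 and 21.

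- m = 2: 1 − 0.97725^12 = 24% per visit; 1 − 0.97725^36 = 56% over three visits.
- m = 3: 1 − 0.99865^12 = 1.6% per visit; 1 − 0.99865^36 = 4.7% over three visits.

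The problem is therefore confined to participants within about 3 SDs of a limit.

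**3. Bazett**

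From the two formulas in SAP 4.9.2.1, QTcB = QTcF × (HR/60)^(1/6). QTcB passes 450 msec at:

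- HR 90: QTcF = 450/(90/60)^(1/6) = 420.6 msec.
- HR 75: QTcF = 450/(75/60)^(1/6) = 433.6 msec.

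Both values satisfy the QTcF entry limit and the 50-90 bpm heart-rate range in exclusion criterion 9.

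**4. Null simulation**

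All inputs are assumptions. In the middle case the QTcF mean is 405-410 msec, the between-participant SD 17, the day-to-day SD 5 and the within-day SD of a triplicate mean 7. Mean heart rate is 64 bpm, with a between-participant SD of about 8. Entry rules are applied to one screening reading, followed by 12 readings on Day -1 and on each dose day.

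| No drug effect | QTcF >450 | QTcB >450 |
|---|---|---|
| Counted per dose visit | 2.5-4.5% | 9-14% |
| The same, out of 36 | 0.9-1.6 | 3.2-5.0 |
| Counted at any of three visits | 4.8-8.1% | 15-23% |
| Share of per-visit counts already >450 on Day -1 | about 48-53% | about 60-64% |
| New onset per visit | 1.3-2.2% | 3.6-5.2% |

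With QTcF means of 400-415, between-participant SDs of 15-20, day-to-day SDs of 4-5 and within-day SDs of 6-8, the per-visit range widens to about 0.5-10.6% for QTcF and 4-23% for QTcB.

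**5. PR and QRS**

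These are also on assumed values, without a separate day-to-day component, as expected counts out of 36 per visit:

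- PR >220: 0.04-0.8 (means 155-165, between-participant SD 20-22, within-participant SD 4-8).
- QRS >120: 0.04-2.4 (means 90-100, between-participant SD 9-10, within-participant SD 2-4).

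**6. Day -1 under the same null**

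The expected Day -1 count equals each dose-day count. For QTcF it is about 2.5% against 2.5% at mean 405, and 4.4% against 4.4% at mean 410.

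**The case against.** The strongest reply is that the design already supplies a fair comparator. Day -1 has the same 12 timepoints and the same device as the dose days, and with no drug effect it has the same expected count. Unconditional counts read against Day -1 are therefore unbiased, and nobody needs to be removed from them. This stands, and it is why those counts should be kept. It does not settle the matter. The SAP does not say that Day -1 will be a column, and two marginal counts do not show who is newly above a limit.

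A reader might go further and ask for treatment-emergent counts in place of the unconditional ones. That would make the contrast worse. New onset is zero on Day -1 by construction, so all residual noise would appear on drug only.

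A reader might also infer that the whole table lacks a baseline reference, or that it could distort the study's conclusion. The documents do not support either reading:

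- QTc increases above 30 and 60 msec, and PR and QRS changes above 25%, are already baseline-referenced.
- SAP 6.4 labels the 450-480 band borderline and cautions that a flagged value need not reflect a clinically significant event.
- The conclusion rests on the model-predicted upper 90% limit (SAP 4.9.2.3). Interval outliers are not an endpoint of the secondary estimand (SAP 2.2).

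Two further points are fair. QTcF is the correction required for clinical decisions, which limits the weight of the QTcB rows, and a heart rate of 90 is the edge of the eligible range. The size of the effect also rests entirely on assumed SDs.

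**Conclusion.** The point holds as a cheap improvement to a descriptive safety table. The absolute limits coincide with the entry limits (for QTc, on QTcF only), and no Day -1 condition is attached to them, although the SAP applies one to morphology in the next paragraph. Part of the on-drug counts will therefore be pre-existing exceedances. In the middle case that is about half of 0.9-1.6 participants out of 36 per visit for QTcF, and about 60-64% of 3.2-5.0 for QTcB. These sizes depend on variability that the documents do not give. PR is little affected under most assumptions, and QRS ranges from negligible to about two participants. No study decision uses this table.

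**What to change.** In SAP 4.12.5 and 6.4:

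- Keep the unconditional counts at every limit.
- State that Day -1, with its 12 timepoints, is a column of the same table.
- Add a new-onset count for each absolute QTcF, QTcB, PR and QRS limit: exceeded at an on-treatment triplicate mean, including the -0.25 h readings on Days 7, 14 and 21, and not exceeded at any of the 12 Day -1 triplicate means.
- Name those 12 means in the rule. SAP 4.12.5 refers to 4.2.4 for the ECG baseline, but 4.2.4 lists only vital signs and laboratory tests as the variables it covers.
- Add a footnote that drug-free against on-drug comparisons should use the unconditional counts, because new onset is zero on Day -1 by construction.

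The cost is one derived flag and extra rows. The Day -1 ECGs are already scheduled. The new-onset count will still contain some noise: on the middle-case assumptions, 1.3-2.2% per visit for QTcF and 3.6-5.2% for QTcB.

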#### **4.12.6 Columbia-Suicide Severity Rating Scale**

As part of the screening procedures, a Columbia Suicide Severity Rating Scale (C-SSRS) will be performed, to assess the risk of suicidal ideation by the prospective participant. Those who show a risk of suicidal ideation will not be included in the study.

The C-SSRS may be repeated during the study at the discretion of the PI.

#### **4.12.7 Physical Examination**

Physical examinations will be performed as shown in section 6.1.

A complete physical examination will include, at a minimum, assessments of the (cardiovascular, respiratory, gastrointestinal, and neurological) systems. Height (at screening) and weight (at screening and discontinuation) will also be measured and recorded. Further, BMI will be calculated from height and weight, and recorded.

A brief physical examination will include, at a minimum, assessments of the skin, lungs, cardiovascular system, and abdomen (liver and spleen).

After screening, any clinically significant abnormal findings in physical examinations should be reported as AEs.

#### **4.12.8 COVID-19 Assessment and COVID-19 AEs**

The overall incidence of AEs and SAEs of COVID-19, COVID-19 AEs leading to study intervention discontinuation will be summarized.

#### **4.12.9 Other Analysis**

Not Applicable.

#### **4.12.10 Daylight Saving Time (DST):**

All scheduled times in ClinBase will be automatically updated to ensure a consistent and protocol-compliant period from the scheduling medication to the actual time point.

#### **4.12.11 Safety Monitoring (Independent Data Monitoring Committee, Data Monitoring Committee, Data and Safety Monitoring Board)**

An Independent Data Monitoring Committee (IDMC) is not required for this study.

### **4.13 Handling of Dropouts or Missing Data**

No imputation of missing data will be performed except for partial dates imputation mention in Section [6.2](#).

#### **4.14 Subgroup Analysis**

No subgroup analysis is planned for this study.

#### **4.15 Planned Interim Analyses**

No interim analysis is planned for this study.

#### 4.16 Determination of Sample Size

At least 36 participants, men or non-pregnant women, aged 18 to 65 years will be enrolled. This number is expected to result in sufficiently wide range of paroxetine concentrations to cover those typically observed in a real-world clinical setting. A Monte Carlo simulation analysis was used to determine the probability of the 90% upper limit of the CI of the  $\Delta QTc$  at the geometric mean of the 60 mg dose encompassing the 10 ms cut-off value. Based on this simulation approach, it is expected that under the assumption of no true effect of paroxetine on QTc at the 60 mg dose, the expected probability of incorrectly detecting an effect (90% upper limit of the CI  $\geq 10$  ms) is <1% (false positive) when inclusion is 36 participants. In case the true effect is 5 ms, the expected probability of a false positive is <2%. When the true effect is 10 ms, the expected probability of correctly determining a QTc prolongating effect is approximately 82%.

The sensitivity to missing data was also assessed. With 20% drop out at the 40 mg dose and another 25% drop out at the 60 mg dose (in addition to the drop out at the 40 mg dose) the expected probability of incorrectly detecting an effect (90% upper limit of the CI 10 msec) for 36 participants is 1% (false positive) when the true effect is null. The expected probability of a false positive is 5% if the true effect is 5 msec. The expected probability of correctly determining a QTc prolonging effect is approximately 85% when the true effect is 10 msec.

The sensitivity of the probability of correctly determining a QTc prolonging effect is calculated with respect to different sample sizes (20, 30, 36, 46, 56) and assuming true effect as 0 msec, 5 msec, and 10 msec.

